9.0 Data and Safety Monitoring Plan

9.1 Periodic evaluation of data

To monitor safety throughout the course of the study, every effort will be made to remain alert to possible Aes/SAEs. If an AE/SAE occurs, the first concern should be for the safety of the subject; CaronTC's medical staff is available 24/7 and will be immediately alerted in the event of a SAE. If necessary, appropriate medical intervention will be provided. At the signing of the written consent form, each subject will have been given the names and telephone numbers of study site staff for reporting Aes/SAEs and medical emergencies.

In this study, any AE/SAE experienced by the subject between the time of first dose of study treatment and 24 hours after the last dose will be recorded on the case report form, regardless of the severity of the event or its relationship to study treatment. During study treatment, the research team will assess the subject for Aes and will record any new Aes/SAEs or updates to previously reported Aes on the electronic case report form.

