1.3 Secondary Study Endpoints

The secondary objective of this pilot study is to evaluate the safety of daily administration of liraglutide in humans seeking treatment for an OUD.

1) Cardiorespiratory Function

- a. *Blood Pressure*. Change in blood pressure from baseline (Day 1) to: i) the beginning of each study drug dose (Days 2, 8, 14, 20, 26); ii) end of the target drug dose (Day 19 [Day 31 for 5-dose intervention]); and iii) rebound follow-up (Day 21 [Day 33 for 5-dose intervention]).
- b. Heart Rate. Change in heart rate from baseline (Day 1) to: i) the beginning of each study drug dose (Days 2, 8, 14, 20, 26); ii) end of the target drug dose (Day 19, [Day 31 for 5-dose intervention]); and iii) rebound follow-up (Day 21 [Day 33 for 5-dose intervention]).
- c. *Respiration*. Change in respiratory from baseline (Day 1) to: i) the beginning of each study drug dose (Days 2, 8, 14, 20, 26); ii) end of the target drug dose (Day 19 [Day 31 for 5-dose intervention]); and iii) rebound follow-up (Day 21 [Day 33 for 5-dose intervention]).

- 2) **Body Weight** (*kg*). Absolute and percent change in body weight from baseline through the end of rebound follow-up (Daily, from Days 1 to 21 [Days 1-33 for 5-dose intervention]).
- 3) **Glycemic Control.** Glycemic control will be monitored by fasting blood samples for fructosamine and A1c. Fasting blood sample measurements change slowly overtime (i.e., across weeks and months) and therefore will be evaluated only on Days 2 and 19 [and additionally Day 31 for 5-dose intervention] via venipuncture.
- 4) Adverse Events. Frequency of adverse events (AE) and serious adverse events (SAE) deemed related to treatment throughout the study period (Days 1-21 [1-33 for 5-dose intervention]), and at 30 days post-intervention (Day 49 [Day 61 for 5-dose intervention]).

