fNIRs data files will be placed into the REDCap database, with access to these files provided to key investigators at Drexel University for signal processing and return for data analyses. These data will be de-identified and will consist only of the unique study id number, raw data, stimulus markers, and date/time stamps that have been modified so that they do not contain the actual visit date.

- **Study drug/placebo administration:** Participants will be taught self-administration by study/nursing staff.
 - All self-administrations will occur via blinded, multi-dose subcutaneous injection pens, and will be observed by nursing staff at CaronTC.
 - Participants will receive medications daily at a specified time (prior to breakfast) throughout the study, starting on Day 2.
 - Participants will be taught to inject the solutions subcutaneously in the abdomen, thigh, or upper arm, and will administer daily injections under the supervision of a study nurse or staff member.
 - Participants will be taught by study staff nurses to attach the needle, check the drug/vehicle flow, select the dose, inject the dose, remove the needle, and dispose of the needle.
 - o Participants will always use a new needle for each dose administration in the study.
- Adverse Events: Adverse events will be monitored continuously throughout the study (Days 1-21 [Days 1-33 for 5-dose intervention]), and at 30 days post-intervention (Day 49 [Day 61 for 5-dose intervention]).

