10.0 Risks

The following risks are associated with the GLP-1R agonist liraglutide during study treatment

Potential risks associated with the study drug: There is a potential risk of experiencing side effects from the investigational drug. Common side effects of liraglutide include: nausea, diarrhea, vomiting, and decreased appetite. These side effects dissipate over time and are minimized with appropriate dose titration. Other potential side effects, though expected to be rare, include: hypoglycemia, constipation, headache, dyspepsia, fatigue, dizziness, abdominal pain, increased lipase, and vaso-vagal response if there is a history of vaso-vagal response. Serious side effects include: risk of thyroid c-cell tumors, acute pancreatitis, acute gallbladder disease, risk of hypoglycemia with concomitant use of anti-diabetic therapy, heart rate increase, renal impairment, and

suicidal behavior and thoughts. There is also potential risk of irritation at the injection site, and increased drug craving in response to needle use.

An allergic reaction to liraglutide can include hives; fast heartbeat, dizziness, trouble breathing or swallowing, and swelling of face, lips, tongue, or throat. There is also potential risk of irritation at the injection site, and increased drug craving in response to needle use. The side effects of acute withdrawal from liraglutide include nausea and vomiting. With a half-life of 13 hours, liraglutide should be completely eliminated in 65 hours, within the 4-day rebound follow-up observation period. Since liraglutide has not been previously used in patients with OUD, it is considered an investigational drug. Since this drug has not been previously given in OUD, there may be risks that are not known at this time.

Overdose of the study drug, according to the literature, is limited to severe nausea and vomiting and occasional abdominal pain and diarrhea. None of the reported cases resulted in hypoglycemia.

Hypoglycemia signs and symptoms

- Feeling shaky
- Being nervous or anxious
- Sweating, chills and clamminess
- Irritability or impatience
- Confusion
- Fast heartbeat
- Feeling lightheaded or dizzy
- Hunger
- Nausea
- Color draining from the skin (pallor)
- Feeling Sleepy
- Feeling weak or having no energy
- Blurred/impaired vision
- Tingling or numbness in the lips, tongue, or cheeks
- Headaches
- Coordination problems, clumsiness
- Difficulty concentrating
- Slurred speech
- Nightmares or crying out during sleep
- Seizures

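### Section 9.1's case-report-form window for adverse events runs from first dose to 24 hours after the last dose, shorter than the adverse-event endpoint's period, and nothing reconciles the two

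*Combined protocol and SAP*

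**What the plan says.** Section 9.1 states that any AE or SAE a participant has "between the time of first dose of study treatment and 24 hours after the last dose will be recorded on the case report form", whatever its severity or cause. The sentence after it also ties AE assessment and electronic case-report-form entry to the treatment period. No other section gives a time window for case-report-form entry.

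Section 1.3, item 4, defines the endpoint as the frequency of treatment-related AEs and SAEs "throughout the study period (Days 1-21 [1-33 for 5-dose intervention]), and at 30 days post-intervention", which it places on Day 49 (Day 61 for 5-dose). Section 7.2 repeats the period: "Adverse events will be monitored continuously throughout the study (Days 1-21 [Days 1-33 for 5-dose intervention]), and at 30 days post-intervention". Sections 7.2.6 and 7.2.10 ask for AEs to be documented up to Day 21 and Day 33. Both schedules of activities mark AEs on Day 1 (after randomization), on the off-drug and rebound days, and at the End of Study call.

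Section 10.0 adds: "The side effects of acute withdrawal from liraglutide include nausea and vomiting". Section 8.3 compares the proportion of participants with AEs and SAEs between arms by chi-square. It gives no window and does not say whether only related events count.

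**The concern.** The protocol describes two periods for the same data. One says which events must go on the case report form; the other says which events the endpoint counts. The first is shorter at both ends, and no text says which governs or how events outside the shorter period reach the analysis dataset.

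Safety is the second study objective (1.1), AE frequency is a named secondary endpoint, and demonstrated safety is a condition for the multi-center phase (2.3). The days at the far end of the gap are the ones the protocol sets aside to look for rebound after stopping. Because 8.3 gives no AE window, the proportion analysed would depend on which section the site staff happened to follow.

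**Working it through.** **Inputs.** First dose is Day 2: "Participants will receive medications daily at a specified time (prior to breakfast) throughout the study, starting on Day 2" (7.2). Last dose is Day 19 for 3-dose (7.2.5) and Day 31 for 5-dose (7.2.8). The call is 30 days, plus or minus 5, after medication stops (7.2.11). The day counts below are for a participant who completes the full schedule.

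**The plan's own figure.** 19 + 30 = 49 and 31 + 30 = 61. Both stated call days reproduce.

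**The 9.1 window laid over the endpoint.**

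| | 3-dose | 5-dose |
|---|---|---|
| 9.1 window | Day 2 to 19 + 1 = Day 20 | Day 2 to 31 + 1 = Day 32 |
| Continuous endpoint days | 1 to 21 | 1 to 33 |
| Covered, counting Day 20/32 as whole | 20 − 2 + 1 = 19 of 21 | 32 − 2 + 1 = 31 of 33 |
| Days wholly outside | Day 1, Day 21 | Day 1, Day 33 |
| End of window to call | 49 − 20 = 29 days | 61 − 32 = 29 days |
| Call inside window? | No | No |

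This count favours the plan. Doses are taken before breakfast, so 24 hours after the last one is the morning of Day 20 (32), and most of that day is outside too.

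**Relation to drug washout.** Section 10.0 gives a 13-hour half-life and elimination by 65 hours (65/13 = 5 half-lives). The fraction of the last dose left at the 9.1 cut-off is 0.5^(24/13) = 0.278, about 28%. Of the 65 hours, 65 − 24 = 41 (41/65 = 63%) come after the cut-off. Since 65 hours is 2 days and 17 hours, a pre-breakfast dose on Day 19 is cleared around the end of Day 21. That is inside the documentation period of 7.2.6 but beyond the window of 9.1. This places the washout relative to the two windows; it does not say when withdrawal symptoms begin or how often they occur.

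**Leverage on the comparison.** With 50 participants randomized 1:1 (8.1, 7.4.3), each arm has about 50/2 = 25. One participant whose only AE falls outside the recorded window moves that arm's proportion by 1/25 = 4 percentage points. A participant who already has an AE inside the window moves it by nothing.

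**The case against.** The best defence is that 9.1 sets a minimum, not a limit. It does not bar later entries, and other sections point to later capture. Sections 7.2.6 and 7.2.10 document AEs through the rebound days, and 9.3 sends safety information to REDCap throughout the study. Section 19.1.2 has the PI confirm, with no time limit, that all AEs are correctly entered on the AE case report forms. SAE reporting in 18.5 has no 24-hour cut-off. One could also suppose two tiers: all-cause recording in 9.1 and longer capture of related events for the endpoint.

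Much of this stands. It rules out saying that late AEs will be lost, and expedited SAE reporting is not affected. It does not remove the conflict: no section states the two-tier reading, and none of the later-capture passages says that it extends the window in 9.1.

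Three stronger readings are tempting and are not supported:

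- **That 29 of 49 days (59%) or 29 of 61 days (48%) of the endpoint are lost.** Those denominators are total participation. The endpoint is continuous only to Day 21 (33), with a single assessment at the call. The documents do not define what period the call looks back over.
- **That withdrawal events would mostly fall after the cut-off.** Section 10.0 gives neither onset time nor frequency.
- **That liraglutide would look safer than it is.** The same cut-off applies to both blinded arms, and anyone with an earlier AE is already counted.

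Day 1 also matters little for an endpoint of treatment-related events, since it precedes the first dose.

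**Conclusion.** The conflict is real and unreconciled. If 9.1 is followed as the recording rule, events on Day 1, most of Day 20 (32), Day 21 (33) and those reported at the call need not reach the case report form. The continuous endpoint period then has 19 of 21 (31 of 33) days covered on the favourable count, and the call is not covered. The AE proportions compared in 8.3 could be understated; the size and any difference between arms cannot be derived from the documents.

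The consequence depends on staff reading 9.1 as the limit of what must be entered. It is a risk to the case report form and the analysis dataset, worth correcting before the data are analysed.

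**What to change.** Amend 9.1 so that all AEs and SAEs from Day 1 through Day 21 (Day 33 for 5-dose), and those reported at the End of Study call (nominally Day 49 or Day 61), are recorded on the case report form. In 8.3, state that the chi-square AE comparison uses this same window, and whether it counts all events or only those judged related, as 1.3 does. Reporting on-treatment and post-treatment events separately would help a reader but is optional.

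The cost is one sentence in 9.1 and one in 8.3. The assessments and the call are already scheduled, and the sample size and power are unchanged.

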9.2 Data that are reviewed

Data collected as primary outcomes, secondary outcomes, exploratory outcomes, and safety profile for the study will be reviewed. Primary outcomes include cue-elicited drug craving and ambient drug craving. Secondary outcomes include blood pressure, heart rate, respiration, body weight, and AE. Exploratory outcomes include prefrontal cortical response to drug cues, markers of long-term glycemic control and rebound in ambient drug craving, blood pressure, heart rate, and respiration.

9.3 Method of collection of safety information

Safety information will be collected in the REDCap research database throughout the study. The safety of the study drug will be evaluated by clinical assessments and laboratory tests.

9.4 Frequency of data collection

Primary outcome data for cue-elicited drug craving will be collected on the day before drug treatment (Day 1) and Day 19 (additionally Day 31 for the 5-dose intervention). Ambient drug craving data will be collected on test days and on the first two days and last 2 days of each treatment dose (Days 1-21 [Days 1-33 for 5-dose intervention]). Secondary outcome data for the physical/psychological screening will be collected on Day 1. Cardiorespiratory function data will be collected periodically throughout the study (Days 1, 2, 8, 14, 19, 21 [5-dose intervention: 1, 2, 8, 14, 20, 26, 31, 33]). HbA1c and fructosamine monitoring (blood draw) data will be collected on Days 2 and 19 [additionally Day 31 for 5-dose intervention]. See also table of study events, section 7.2.

9.5 Individuals reviewing the data

The DSMB will be responsible for safeguarding the interests of participants in this trial. This responsibility will be exercised by providing recommendations for continuation or early termination of the trial, based on assessment of safety. The DSMB may also formulate recommendations related to the selection, recruitment or retention of participants, their management and adherence to protocol-specified interventions, and the procedures for data management and quality control. The DSMB will be advisory to the PI, to the medical monitor ([name]), and to their co-investigators. The PI will be responsible for promptly reviewing and implementing DSMB recommendations.

The DSMB will consist of at least 3 independent experts who have no conflicts of interest. Members of the DSMB will include [name], a cardiologist and clinician scientist with expertise in mechanisms of neurocirculatory control, broad clinical experience and a track record of clinical research, translational research, human studies and clinical trials at Penn State University; [name], a board-certified physician in internal medicine and endocrinology, currently practicing at the Penn State Health Cocoa Outpatient Center; and [name], a professor in biostatistics in the Public Health Sciences department at the Penn State College of Medicine that has served on many DSMBs for the NIH-or industry-sponsored clinical trials. Representation from the Office of Patient Oriented Research (OPOR) also will participate. The approval of the DSMB will be required for any significant changes in protocol recommended by the clinical Project PI, on consultation with Study Physicians, during the course of the study.

The DSMB membership will be restricted to individuals who have no apparent financial, scientific or regulatory conflicts of interest. DSMB members are expected to declare any other potential conflicts of interest so that other members can judge whether any such conflicts might affect objectivity. Members who develop significant conflicts of interest during the course of the trial are expected to resign from the DSMB. DSMB members are otherwise expected to continue their participation until the trial is closed. If necessary, the PI will appoint replacements for any DSMB members who resign, subject to concurrence of the remaining DSMB members.

9.6 Frequency of review of cumulative data

Safety is constantly monitored during the study and any concerns are brought to the attention of the PI immediately. Summary data will be provided at least once per month to the medical monitor to review recruitment and enrollment, protocol adherence, data quality, and Aes. The Aes will be documented and reported appropriately according to the Human Subjects Protection Office (HSPO) policies and procedures.

The DSMB will meet every 6 months with the PI, or more often if needed. In preparation for these meetings, the PI will provide information by email regarding enrollment, protocol adherence, and data quality. The DSMB will also assess safety data including common and serious AE. In the case of an unanticipated or serious AE, the DSMB will be notified within 24 hours of the PI's notification of the event. The PI will provide the DSMB with a list of non-serious AE during regularly scheduled meetings.

9.7 Statistical tests

For details, see the statistical section under 8.3.

9.8 Suspension of research

After periodic evaluation of study result and safety profile, the PI can terminate the research anytime based on outcomes of periodic safety monitoring and benefit/risk outcomes and would be assessed with the IRB and DSMB.

10.0 Risks

The following risks are associated with the GLP-1R agonist liraglutide during study treatment

Potential risks associated with the study drug: There is a potential risk of experiencing side effects from the investigational drug. Common side effects of liraglutide include: nausea, diarrhea, vomiting, and decreased appetite. These side effects dissipate over time and are minimized with appropriate dose titration. Other potential side effects, though expected to be rare, include: hypoglycemia, constipation, headache, dyspepsia, fatigue, dizziness, abdominal pain, increased lipase, and vaso-vagal response if there is a history of vaso-vagal response. Serious side effects include: risk of thyroid c-cell tumors, acute pancreatitis, acute gallbladder disease, risk of hypoglycemia with concomitant use of anti-diabetic therapy, heart rate increase, renal impairment, and

suicidal behavior and thoughts. There is also potential risk of irritation at the injection site, and increased drug craving in response to needle use.

An allergic reaction to liraglutide can include hives; fast heartbeat, dizziness, trouble breathing or swallowing, and swelling of face, lips, tongue, or throat. There is also potential risk of irritation at the injection site, and increased drug craving in response to needle use. The side effects of acute withdrawal from liraglutide include nausea and vomiting. With a half-life of 13 hours, liraglutide should be completely eliminated in 65 hours, within the 4-day rebound follow-up observation period. Since liraglutide has not been previously used in patients with OUD, it is considered an investigational drug. Since this drug has not been previously given in OUD, there may be risks that are not known at this time.

Overdose of the study drug, according to the literature, is limited to severe nausea and vomiting and occasional abdominal pain and diarrhea. None of the reported cases resulted in hypoglycemia.

Hypoglycemia signs and symptoms

- Feeling shaky
- Being nervous or anxious
- Sweating, chills and clamminess
- Irritability or impatience
- Confusion
- Fast heartbeat
- Feeling lightheaded or dizzy
- Hunger
- Nausea
- Color draining from the skin (pallor)
- Feeling Sleepy
- Feeling weak or having no energy
- Blurred/impaired vision
- Tingling or numbness in the lips, tongue, or cheeks
- Headaches
- Coordination problems, clumsiness
- Difficulty concentrating
- Slurred speech
- Nightmares or crying out during sleep
- Seizures
- Loss of consciousness

Blood Pressure and Heart Rate: Frequent blood pressure measurements with the cuff around the arm or finger may be inconvenient and may produce some discomfort and occasional bruising of the upper arm. There is a minimal risk of skin irritation from the EKG patches.

Blood Sampling: There are minor risks and discomforts associated with blood sampling. We will draw blood from the antecubital veins which may cause a brief period of pain and possibly a small bruise at the site. Occasionally, a person feels faint when their blood is drawn. There is a small risk of bleeding after removal of the needle, which can be prevented by tight compression. Rarely, an infection develops which can be treated. Rarely, a clot could form. It is possible that exposure to needles during blood sampling may serve as a trigger for opioid use for some participants.

Pregnancy: This treatment may hurt an unborn child. Subjects will be advised to use approved birth control such as birth control pills, birth control shots, IUD, diaphragm, or condoms while in this study. Subjects will be instructed to inform us if they become pregnant or father a child while in this study. Women able to become pregnant will have a urine test to make sure they are not pregnant before receiving treatment in this study and

at Day 19 [an additional pregnancy test will be given at Day 31 for the 5-dose intervention]. They will be encouraged to use birth control or refrain from intercourse throughout the study. Study drug will be discontinued in case of pregnancy.

Potential risks associated with exposure to drug-related cues: There is a risk of relapse to those in recovery when they are exposed to drug cues in the cue reactivity task. Participants may experience an increase in craving in response to opioid-related images.

Risks related to exposure to fNIRs: There are no known discomforts or risks associated with the brain imaging study. Risks of fNIRs were previously found to be minimal. FDA approval has been granted for research purposes for the technology that is used in this specific device (FDA 510(K) Numbers K011320; K042501). In this fNIRs Devices system: 1) No voltage in excess of 12.2 volts is available; 2) The sensor pads can be washed, disinfected and autoclaved; 3) The safety of fNIRs for use on brain tissue can be demonstrated by comparing the risks associated with experimental exposure to everyday risks. The instrument used in the current research employs light emitting diodes (LEDs) to generate the near infrared light for measuring changes in hemoglobin. LEDs are electronic devices that are illuminated when electricity is passed through them. LEDs use a semiconductor diode that emits light when charged. There currently exists no specific safety regulations applied to LEDs, although they fall within the Class I standards for safety. In other words, the risks associated with spending 20-30 minutes in a protocol utilizing fNIRs are less than the risks associated with spending an equivalent amount of time in the sunlight in the US without a hat. In summary, exposing the brain to the infrared light generated by these LEDs poses no greater risk than spending an equivalent amount of time (about 1 hour) exposed to sunlight. There is minimal risk of headache from the use of sensors.

Actigraphy/Wearables: There is no known risk to wearing the wrist actigraphs. A minor skin rash may develop from the wristband, but this risk is very slight.

Questionnaires: The interviews and forms are routine, standardized forms for psychology research. They pose no known risks, although certain questions may be mildly upsetting because they may probe sensitive psychological areas and others inquire about family history of medical and psychological illness or alcohol and substance use. Appropriate referrals are offered if areas of concern arise in the course of collecting this information. Research participants are free to skip any questions that make them uncomfortable.

Other risks

There is a risk that blood tests will reveal that patients are positive for hepatitis or HIV. These infections are required by law to be reported to the Pennsylvania Department of Health.

There is a risk of loss of confidentiality if a patient's information or identity is obtained by someone other than the investigators, but precautions will be taken to prevent this from happening. The confidentiality of the patients' electronic data will be maintained as required by applicable law and to the degree permitted by the technology used. Absolute confidentiality cannot be guaranteed.

There is a risk from randomization as patients will be assigned to a treatment program by chance. The treatment a patient receives may prove to be less effective or to have more side effects than the other research treatment or other available treatments.

